4.5. EARLY STUDY TERMINATION

The study may be terminated early at the discretion of the Sponsor. Circumstances that may warrant early termination include:

- Observation of an unexpected, significant risk to subjects
- Failure to enroll subjects at an acceptable rate
- Plans to modify, suspend, or discontinue the development of study drug

5. STUDY DRUG MATERIALS AND MANAGEMENT

5.1. DESCRIPTION OF BEZUCLASTINIB

There are 2 formulations of bezuclastinib described as Formulation A (original) and Formulation B (modified). Bezuclastinib Formulation A are wide, flat, oblong-shaped tablets, and available in a 50 mg strength for oral administration. Bezuclastinib Formulation B are capsule-shaped tablets, and available in a 50 mg strength for oral administration. Prior to the start of the study, the Sponsor will provide labeled supplies of bezuclastinib to the site investigational pharmacy.

Bezuclastinib will be supplied in bottles containing 50 mg tablets. The study drug is to be stored at controlled room temperature (not above 25°C/77°F).

Bezuclastinib will be labeled and packaged in an open-label fashion in accordance with Good Manufacturing Practices for clinical trials and country-specific guidelines.

Refer to the Pharmacy Manual and the current edition of the IB for further information on the study drug.

5.2. BEZUCLASTINIB ADMINISTRATION

Bezuclastinib will be administered as single agent 50 mg tablets. Since the bioavailability of Formulation A is limited by absorption and food has been shown to increase the oral bioavailability (PLX121-02), subjects participating in Part 1 will be instructed to take their assigned dose of study drug with food and water to maximize exposure. As higher exposure and faster absorption were observed with Formulation B relative to Formulation A (Study CGT9486-21-101), the exposure achieved in Part 1 with Formulation A under fed conditions can be achieved with Formulation B under fasted conditions at a similar or lower QD dose level. Therefore, subjects participating in Part 2 will be instructed to take their assigned dose of study drug on an empty stomach (at least 1 hour before or 2 hours after a meal). With either formulation, the entire dose should be taken within 30 minutes at approximately the same time each day. The dose taken should be recorded in the provided study drug diary. Bezuclastinib tablets should not be broken, crushed, or dissolved in solution.

For dose cohorts with a BID schedule (Part 1), the bezuclastinib doses should be taken approximately 12 hours apart (± 3 hours). For dose cohorts with a QD schedule, the bezuclastinib doses should be taken approximately 24 hours apart (± 6 hours). Missed or skipped doses should not be made up. One treatment cycle is 28 days. Treatment will be continuous; there will be no gaps between cycles.

On days of a scheduled clinic visit, subjects should be instructed to take study drug at the clinic after visit procedures and assessments are performed.

5.3. RANDOMIZATION

This is a randomized, open-label study. Subjects in Part 1 will be randomized to receive bezuclastinib Formulation A in a 1:1:1:1 (50 mg BID:100 mg BID:200 mg BID:400 mg QD)

manner. Randomization will be stratified by evaluability per modified IWG-MRT-ECNM response criteria (ie, evaluable vs non-evaluable).

Subjects in Part 2 Stage 1 will be randomized to receive bezuclastinib Formulation B in a 1:1 (150 mg QD:300 mg QD) manner. Randomization will be stratified by prior treatment of TKI (ie, yes vs no).

Subjects in Part 2 Stage 2 will receive bezuclastinib at the selected dose based on the totality of clinical data from Part 1 and Part 2 Stage 1.

5.4. TREATMENT COMPLIANCE

At each applicable visit, subjects will be given an adequate supply of study drug so that the subject will have enough doses until the next applicable visit. Study drug diaries will be provided to subjects at applicable study visits and used to track bezuclastinib administration.

Compliance for doses taken outside of the clinic will be assessed by a count of the tablets returned to the study trial site by the subject and reviewed with the subject.

5.5. STUDY DRUG ACCOUNTABILITY

The Investigator or designee is responsible for taking an inventory of each shipment of bezuclastinib investigational supplies received and comparing it with the accompanying drug accountability form.

Subjects will be instructed to bring all unused bezuclastinib tablets, empty bottles, and their study drug diary to each study visit. The study site will count all tablets that the subject returns, review the study drug diary, and account for taken doses, missed doses, doses reduced due to missing or lost tablets, etc. before dispensing new study drug to the subject. Any subject who does not take the prescribed dose will be requested to return the remaining drug to the clinical trial site for accountability.

All unused bezuclastinib will be retained at the site. After full drug accountability and reconciliation, the Investigator will dispose of the study drug at the clinical trial site according to site procedures, or at the Sponsor's request, will return all bezuclastinib to the Sponsor or its designee. If any study drug is lost or damaged, the disposition of the study drug should be documented.

5.6. CRITERIA FOR DOSE MODIFICATION

When treatment-related toxicities are observed, dosing with bezuclastinib may be interrupted until recovery from the observed treatment-related toxicities, and to consider if dose reductions are appropriate for continued therapy with bezuclastinib. Please refer to [Table 5](#) for dose modification guidance for Formulation A and Formulation B. Repeated dose reductions are permitted; however, doses below 50 mg QD are not allowed. Subjects who are unable to tolerate bezuclastinib 50 mg QD will be discontinued from treatment. Subjects who require a dose reduction due to a treatment-related toxicity may have their bezuclastinib dose re-escalated if they are on the reduced dose for more than 28 days without recurrence of the observed toxicity

and with no new treatment-related events requiring dose modification. If another treatment-related event requiring a dose reduction occurs, the subject will not be allowed to re-escalate the dose again unless it is in the best interest of the subject per the Investigator and agreed to by the Sponsor. The Sponsor should be promptly informed prior to any decision to hold or change subject dosing.

Table 5: Bezuclastinib Dose Cohorts

	Bezuclastinib Dose Table					
	Formulation A (Part 1)				Formulation B (Part 2)	
	Dose Cohort 1	Dose Cohort 2	Dose Cohort 3	Dose Cohort 4		
Initial dose	50 mg BID	100 mg BID	200 mg BID	400 mg QD	150 mg QD	300 mg QD
First dose reduction	50 mg QD	50 mg BID	100 mg BID	200 mg QD	100 mg QD	150 mg QD
Second dose reduction	NA	50 mg QD	50 mg BID	100 mg QD	50 mg QD	100 mg QD
Third dose reduction	NA	NA	50 mg QD	50 mg QD	NA	50 mg QD

Abbreviations: BID=twice daily, NA=not applicable; QD=once daily.

A dose interruption of up to 28 days is allowed for TEAEs considered to be at least possibly related to study drug to return to ≤ Grade 1 or Baseline. TEAEs that are possibly related to study drug and require dose interruptions of more than 28 days will result in the permanent discontinuation of bezuclastinib.

Recommended dose modifications for TEAEs considered to be at least possibly related to study drug are provided in Table 6.

For risk management recommendations associated with the important potential risks of bezuclastinib, please refer to Section 6.2.4 of the current edition of the IB.

Table 6: Dose Modification Criteria for TEAEs At Least Possibly Related to Bezuclastinib

TEAE	Criteria or CTCAE v5.0 Grade	Dose Modification
Anemia, neutropenia, thrombocytopenia (a)	Grade 4 anemia for ≥7 days Grade 4 neutropenia for ≥7 days, or Grade 3 or worse neutropenia associated with bacterial or fungal infection requiring systemic therapy Febrile neutropenia (any grade) Grade 4 thrombocytopenia for ≥7 days, or Grade 3 or worse thrombocytopenia associated with bleeding	Hold bezuclastinib until resolved to ≤Grade 1 or baseline. If recovered to ≤Grade 1 or baseline in ≤28 days, reduce by 1 dose level. If not recovered to ≤Grade 1 or baseline after 28 days, discontinue study drug.

Table 6: Dose Modification Criteria for TEAEs At Least Possibly Related to Bezuclastinib

TEAE	Criteria or CTCAE v5.0 Grade	Dose Modification
ECG QT prolonged	Grade 3: >500 msec or >60 msec increase from baseline (b)	Hold bezuclastinib until QTc ≤500 msec (≤Grade 2); then reduce by 1 dose level If not recovered to ≤Grade 1 or baseline after 28 days, discontinue study drug.
	Grade 4: Torsade de pointes, polymorphic ventricular tachycardia, or signs/symptoms of serious arrhythmia	Permanently discontinue study drug.
Transaminase increases	ALT or AST >8×ULN ALT or AST >5×ULN for more than 2 weeks ALT or AST >3×ULN and TBL >2×ULN or INR >1.5 ALT or AST >3×ULN with the appearance of fatigue, nausea, vomiting, right upper quadrant pain or tenderness, fever, rash, and/or eosinophilia (>5%)	Consider the possibility of drug-induced liver injury. If drug-induced liver injury is suspected, permanently discontinue study drug if it is in the best interest of the subject.
Other non-hematological toxicity (excluding Grade 3 nausea, vomiting, or diarrhea lasting ≤72 hours with adequate prophylactic and supportive care), including clinically significant non-hematologic laboratory parameters (excluding elevations in alkaline phosphatase)	Grade 3	Hold bezuclastinib until resolved to ≤Grade 1 or baseline. If recovered to ≤Grade 1 or baseline in ≤28 days, reduce by 1 dose level. If not recovered to ≤Grade 1 or baseline after 28 days, discontinue study drug.
	Grade 4	Permanently discontinue study drug unless considered unrelated to treatment.

Abbreviations: AE=adverse event, ALT=alanine transaminase, AST=aminotransferase, CTCAE=National Cancer Institute Common Terminology for Adverse Events, ECG=electrocardiogram, MCL=mast cell leukemia, QTc=corrected QT interval, TBL=total bilirubin, TEAE=treatment-emergent adverse event, ULN=upper limit of normal.

- (a) For subjects with MCL or subjects for whom Grade 3 cytopenia was recorded at Screening due to disease progression, a Grade 3 or Grade 4 event of cytopenia may not require dose interruption/modification, following discussion with the Investigator and Medical Monitor.
- (b) Triplicate readings are required.

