Pharmacokinetic and Pharmacodynamic Assessments

Blood samples will be collected for determination of bezuclastinib PK. Blood and bone marrow will be collected for analysis of the clinical and pharmacodynamic effects of bezuclastinib.

Criteria for Dose Modifications in Part 1 and Part 2

When treatment-related toxicities are observed, dosing with bezuclastinib may be interrupted until recovery from the observed treatment-related toxicities, and to consider if dose reductions are appropriate for continued therapy with bezuclastinib. Please refer to the Bezuclastinib Dose Table below for dose modification guidance for Formulation A and Formulation B. Repeated dose reductions are permitted; however, doses below 50 mg QD are not allowed. Subjects who are unable to tolerate bezuclastinib 50 mg QD will be discontinued from treatment. Subjects who require a dose reduction due to a treatment-related toxicity may have their bezuclastinib dose re-escalated if they are on the reduced dose for more than 28 days without recurrence of the observed toxicity and with no new treatment-related events requiring dose modification. If another treatment-related event requiring a dose reduction occurs, the subject will not be allowed to re-escalate the dose again unless it is in the best interest of the subject per the Investigator and agreed to by the Sponsor.

	Bezuclastinib Dose Table					
	Formulation A (Part 1)				Formulation B (Part 2)	
	Dose Cohort 1	Dose Cohort 2	Dose Cohort 3	Dose Cohort 4		
Initial dose	50 mg BID	100 mg BID	200 mg BID	400 mg QD	150 mg QD	300 mg QD
First dose reduction	50 mg QD	50 mg BID	100 mg BID	200 mg QD	100 mg QD	150 mg QD
Second dose reduction	NA	50 mg QD	50 mg BID	100 mg QD	50 mg QD	100 mg QD
Third dose reduction	NA	NA	50 mg QD	50 mg QD	NA	50 mg QD

Abbreviations: BID=twice daily, NA=not applicable, QD=once daily.

A dose interruption of up to 28 days is allowed for treatment-emergent adverse events (TEAEs) considered to be at least possibly related to study drug to return to \leq Grade 1 or Baseline. TEAEs that are considered at least possibly related to study drug and require dose interruptions of more than 28 days will result in the permanent discontinuation of bezuclastinib.

Recommended dose modifications for TEAEs considered at least possibly related to study drug are provided in the following table.

Dose Modification Criteria for TEAEs At Least Possibly Related to Bezuclastinib		
TEAE	Criteria or CTCAE v5.0 Grade	Dose Modification

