Anemia, neutropenia, thrombocytopenia (a)	Grade 4 anemia for ≥ 7 days Grade 4 neutropenia for ≥ 7 days, or Grade 3 or worse neutropenia associated with bacterial or fungal infection requiring systemic therapy Febrile neutropenia (any grade) Grade 4 thrombocytopenia for ≥ 7 days, or Grade 3 or worse thrombocytopenia associated with bleeding	Hold bezuclastinib until resolved to \leq Grade 1 or baseline. If recovered to \leq Grade 1 or baseline in ≤ 28 days, reduce by 1 dose level. If not recovered to \leq Grade 1 or baseline after 28 days, discontinue study drug.
ECG QT prolonged	Grade 3: >500 msec or >60 msec increase from baseline (b)	Hold bezuclastinib until QTc ≤ 500 msec (\leq Grade 2); then reduce by 1 dose level If not recovered to \leq Grade 1 or baseline after 28 days, discontinue study drug.
	Grade 4: Torsade de pointes, polymorphic ventricular tachycardia, or signs/symptoms of serious arrhythmia	Permanently discontinue study drug.
Transaminase increases	ALT or AST $>8 \times$ ULN ALT or AST $>5 \times$ ULN for more than 2 weeks ALT or AST $>3 \times$ ULN and TBL $>2 \times$ ULN or INR >1.5 ALT or AST $>3 \times$ ULN with the appearance of fatigue, nausea, vomiting, right upper quadrant pain or tenderness, fever, rash, and/or eosinophilia ($>5\%$)	Consider the possibility of drug-induced liver injury. If drug-induced liver injury is suspected, permanently discontinue study drug if it is in the best interest of the subject.
Other non-hematological toxicity (excluding Grade 3 nausea, vomiting, or diarrhea lasting ≤ 72 hours with adequate prophylactic and supportive care), including clinically significant non-hematologic	Grade 3	Hold bezuclastinib until resolved to \leq Grade 1 or baseline. If recovered to \leq Grade 1 or baseline in ≤ 28 days, reduce by 1 dose level. If not recovered to \leq Grade 1 or baseline after 28 days, discontinue study drug.

laboratory parameters (excluding elevations in alkaline phosphatase)	Grade 4	Permanently discontinue study drug unless considered unrelated to treatment.

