4.2. EXCLUSION CRITERIA

Subjects will not be eligible for inclusion in this study if any of the following criteria apply:

1. Persistent toxicity from previous therapy for AdvSM that has not resolved to \leq Grade 1.
2. Patients presenting with an associated hematologic neoplasm who require immediate antineoplastic therapy.
3. Clinically significant cardiac disease, defined by any of the following:
 - a. Uncontrolled or untreated cardiac arrhythmias
 - b. Congenital long QT syndrome or concomitant medications known to prolong the QT interval except those required for infections that carry a low risk of QTc prolongation.
 - c. A marked baseline prolongation of QT/QTc interval (eg, repeated demonstration of a QTcF [QT corrected using Fridericia's formula] interval > 480 msec).
 - d. History of clinically significant cardiac disease or congestive heart failure $>$ New York Heart Association Class II. (Patients must not have unstable angina [anginal symptoms at rest] or new-onset angina within the last 3 months or myocardial infarction within the past 6 months.)
 - e. Arterial or venous thrombotic or embolic events such as cerebrovascular accident (including transient ischemic attacks), deep vein thrombosis, or pulmonary embolism within the 6 months before study drug initiation (except for adequately treated catheter-related venous thrombosis occurring more than 1 month before the first dose of study drug).
4. Known positivity for the *FIP1L1-PDGFR*A fusion (except for patients who demonstrated relapse or disease progression on prior imatinib therapy). Patients with eosinophilia (eosinophil count $> 1.5 \times 10^9/\text{L}$) who do not have a detectable *KIT* D816V mutation must provide documentation of the lack of a PDGFR A fusion mutation by fluorescence in situ hybridization or polymerase chain reaction prior to enrollment.

5. Any other concurrent severe known disease or concurrent severe and/or uncontrolled medical condition (eg, uncontrolled diabetes or active uncontrolled infection), either of which could compromise participation in the study.
6. Seropositive for human immunodeficiency virus (HIV) 1 or 2, positive for hepatitis B surface antigen, or positive for hepatitis C virus (HCV) antibody. (Subjects with a positive HCV antibody may be eligible if HCV RNA is undetectable on a quantitative HCV RNA assay, following discussion with the Medical Monitor.)
7. Active, uncontrolled, systemic bacterial, fungal, or viral infections at Screening.

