4.3. SUBJECT WITHDRAWAL CRITERIA

4.3.1. Treatment Discontinuation for Individual Subjects

Treatment discontinuation is defined as an instance in which a subject permanently stops receiving study drug and does not restart drug. Subjects who experience a TEAE that is assessed as at least possibly related to study drug and require a dose interruption of more than 28 days must permanently discontinue treatment with bezuclastinib. A subject should be discontinued from study treatment if, in the opinion of the Investigator or Sponsor, it is medically necessary to do so, or if it is the wish of the subject. A subject who becomes eligible for hematopoietic stem cell transplantation (HSCT) and for whom HSCT is the most appropriate therapeutic option should discontinue treatment and receive HSCT at the discretion of the Investigator.

A subject must discontinue study treatment for:

- Protocol-specified documented disease progression
- Investigator decision
- Subject withdrawal of consent
- Development of an AE, that in the opinion of the Investigator, would render continued participation harmful to the subject
- Subject pregnancy
- Lost to follow up (ie, inability by the Investigator to contact and/or effectively monitor the subject)
- Termination of study by Sponsor
- Enrollment in another therapeutic study
- Receiving a non-protocol-approved treatment plan for treatment of the subject's AdvSM

The Sponsor is to be immediately notified if a subject discontinues study treatment for any reason. The reason for treatment discontinuation must be documented on the appropriate electronic case report form (eCRF). Noncompliance with the protocol medication/treatments and/or required follow-up, as judged by the Investigator, may result in discontinuation of study drug.

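### The QT row's restart figure (QTc ≤500 msec) covers only one of its two Grade 3 triggers, so for baselines below 440 msec the number and the bracketed grade disagree

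*Protocol*

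**What the plan says.** The ECG QT prolonged row of Table 6 (Protocol 5.6) sets the Grade 3 trigger as "Grade 3: >500 msec or >60 msec increase from baseline (b"; the trailing letter points to a footnote requiring triplicate readings. Either limb is enough. The action is "Hold bezuclastinib until QTc ≤500 msec (≤Grade 2); then reduce by 1 dose level", followed by a stop rule: "If not recovered to ≤Grade 1 or baseline after 28 days, discontinue study drug".

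The dose modification table in the synopsis carries the same row, with the same two-limb trigger and the same ending, "then reduce by 1 dose level".

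Three other places bear on how the row is read:

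- The 5.6 text before the table, also in the synopsis, allows interruptions of up to 28 days for events "at least possibly related to study drug to return to ≤ Grade 1 or Baseline". It introduces Table 6 as recommended modifications, and it asks that the Sponsor be informed before any decision to hold or change dosing.
- Exclusion criterion 3c (4.2) removes "A marked baseline prolongation of QT/QTc interval", with repeated QTcF above 480 msec as its example. It sets no lower limit.
- Section 7.1.3 lists QTc prolongation of Grade 3 or higher as an adverse event of clinical interest.

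**The concern.** A rule that starts a hold on either of two conditions should end it only when both have cleared. This row gives a release value for the absolute limb alone, and labels that value as Grade 2 or lower. Under the row's own trigger the label is not always true.

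The plainest case is a subject held only because QTc rose by more than 60 msec while staying at or below 500 msec. That subject already meets the numeric restart figure when the hold begins. A subject held for a QTc above 500 msec can be affected as well, if QTc falls below 500 but stays far above baseline.

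At stake is patient safety wording. A site that works from the number could restart bezuclastinib, one dose level lower, while the event is still Grade 3.

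**Working it through.** No sample-size or power figure is involved; the check is threshold logic on the row's own definitions.

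**Inputs**

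- Grade 3 trigger (Table 6 and synopsis): QTc > 500 or QTc − b > 60, where b is baseline QTc in msec.
- Numeric restart figure (Table 6 and synopsis): QTc ≤ 500, labelled ≤Grade 2.
- Eligible baselines (4.2, criterion 3c): no lower limit, so values below 440 msec are admissible. The individual baselines below are assumptions, because the protocol gives no QTc distribution.

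**Where the plan's figure works.** If b ≥ 440, then b + 60 ≥ 500. Any QTc ≤ 500 then means a rise of at most 60 msec, so neither Grade 3 limb is met. For these baselines the printed number and the bracketed grade agree.

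**Where it does not.** The number is met while the event is still Grade 3 when

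b + 60 < QTc ≤ 500.

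This has a solution only if b + 60 < 500, that is b < 440. The width of the band is 500 − (b + 60) = 440 − b. The restart value consistent with both limbs is min(500, b + 60).

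| Baseline b (msec) | QTc that meets ≤500 but is still Grade 3 (whole msec) | Width (msec) | Rise at QTc 500 (msec) | Restart value meeting both limbs (msec) |
|---|---|---|---|---|
| 380 | 441 to 500 | 60 | 120 | ≤440 |
| 400 | 461 to 500 | 40 | 100 | ≤460 |
| 420 | 481 to 500 | 20 | 80 | ≤480 |
| 430 | 491 to 500 | 10 | 70 | ≤490 |
| 439 | 500 only | 1 | 61 | ≤499 |
| 440 | none | 0 | 60 | ≤500 |
| 450 to 480 | none | 0 | 50 to 20 | ≤500 |

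**Two worked cases**

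- Held on the rise limb: b = 420, QTc = 485. Rise = 485 − 420 = 65 > 60, so Grade 3. Yet 485 ≤ 500, so the number is met from the first day of the hold.
- Held on the absolute limb: b = 400, QTc falls from 510 to 495. The number is now met, but the rise is 495 − 400 = 95 > 60, so the event is still Grade 3.

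**The case against.** The strongest reply is that the bracket controls. The row prints both the number and the grade, and Grade 3 is defined in the adjacent cell. At baseline 400 and QTc 495 the event is Grade 3, the bracket is not met, and dosing should not resume. A hold that ended as it began would also make no sense, and 5.6 opens by describing interruption until the toxicity has recovered. This stands to the extent that a reader who grades first is protected. It does not make the number right: the bracket reads as a gloss on the figure, and nothing says which prevails when they differ.

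Other safeguards also limit the risk. Table 6 is a recommendation, the Sponsor is to be informed first, and ECGs go to central review (6.10). Congenital long QT and, with a limited exception, QT-prolonging medication are excluded (4.2, criterion 3b). The nonclinical section (1.2.1) reports no hERG inhibition up to the solubility limit, and QT is not among the important potential risks in 1.4. These reduce the likely number of affected subjects; they do not correct the wording.

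A reader might infer two further faults, and the documents support neither.

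- *The Grade 2 restart contradicts the Grade 1 or baseline target in 5.6.* That sentence caps the length of an interruption and states its purpose in general terms. A specific row may set its own restart level. The transaminase row already departs from the pattern, with no hold or recovery target.
- *The 28-day stop contradicts restarting at Grade 2.* The two lines can be read in order. The row does not say whether the stop still applies after restart, but that is an ambiguity, not a conflict. Section 4.3.1 says that subjects whose related events "require a dose interruption of more than 28 days must permanently discontinue treatment with bezuclastinib", which makes a long interruption a sufficient ground for stopping and not the only one.

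**Conclusion.** The point holds for the restart figure alone. The 440 msec cut-off is exact and follows from the row's own two thresholds. How many subjects fall in the band cannot be computed: the documents give neither baseline QTc values nor an expected frequency of Grade 3 QT events. Given the safeguards, few are likely to be affected.

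It would go too far to say that the protocol permits dosing during a Grade 3 event. The bracketed grade forbids it, and the fault is that the number beside it says otherwise. It is still worth correcting because this is a stated decision threshold, wrong as written for part of the eligible range, on an event the protocol singles out for clinical interest. No sample size, endpoint or analysis is touched.

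**What to change.** In the Grade 3 QT row of Table 6 and in its synopsis copy, add the second limb to the restart figure. The hold then lasts until QTc is ≤500 msec and ≤60 msec above baseline (≤Grade 2), with the one-level dose reduction kept as it is.

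Leave the 28-day line and the 5.6 interruption sentence unchanged. Making the 28-day stop apply after restart would be a clinical choice that the documents do not settle, since it could remove a subject who is stable at Grade 2 on a reduced dose.

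The cost is one short phrase in two places, with no new procedure: the baseline ECG needed for the comparison is already required by the trigger.
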